10.4. Analysis Populations

10.4.1. Safety Analysis Population

The safety analysis population will consist of all randomized patients who received the study treatment (and examet or usual care) and analyzed according to the actual treatment received.

10.4.2. Efficacy Analysis Population

Intent-to-Treat Population (ITT): The ITT Population will include all randomized patients according to the randomized treatment. Participants who are randomized without signing the consent form throughout the study will not be included in the ITT set.

Per-Protocol Population (PP): The PP Population will include all patients in the ITT population who did not have important protocol deviations which impact the primary efficacy assessment.

The full definition of the PP set is provided in the SAP.

10.4.3. Patient Disposition

Patient disposition, including total screened, enrolled, randomized, early terminations, and withdrawals, will be presented by treatment assignment. In addition, a listing will be providing with the reasons for screen failures and study discontinuations.

10.4.4. Baseline and Demographic Characteristics

Baseline and demographic characteristics will be summarized for both the safety and efficacy populations. Data will be summarized using descriptive statistics of frequencies for categorical data and means, medians, standard deviations, minimums, and maximums for continuous data. No inferential analyses of these data are planned.

10.4.5. Treatment Compliance

Patient compliance with the assigned treatment will not be evaluated since all procedures are performed in the hospital by a trained professional (for andexanet, any dose modifications will also be recorded and presented). However, lack of compliance or deviation from the study required evaluations will be listed.

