4.0 SELECTION OF STUDY POPULATION AND CRITERIA FOR WITHDRAWAL

4.1. Inclusion Criteria

To be eligible for study enrollment, potential study patients must satisfy all of the following inclusion criteria:

- 1. Written informed consent. Either the patient or his or her legally authorized representative (LAR) if permissible by local or regional laws and regulations has been adequately informed of the nature and risks of the study and has given written informed consent prior to Screening.
 - Deferred consent procedure is allowed where approved by local ethics committees. In cases of deferred consent, the time of the study physician's documented decision to include the patient into the study will serve as "time of consent" with respect to protocol-specific procedures.
 - In all cases where the patient does not sign informed consent prior to study entry, informed consent from the patient (or LAR) will be obtained as soon as realistically possible after inclusion in the trial and in accordance with the Declaration of Helsinki, International Council for Harmonisation of Technical Requirements for Pharmaceuticals for Human Use (ICH) Good Clinical Practice (GCP), the EU General Data Protection Regulation (GDPR), and national and local regulations.
- 2. Age \geq 18 years old at the time of consent.
- An acute intracerebral bleeding episode, defined as an estimated blood volume ≥ 0.5 to ≤ 60 mL acutely observed radiographically within the cerebrum. Patients may have extracerebral (e.g., subdural, subarachnoid, epidural) or extracranial (e.g., gastrointestinal, intraspinal) bleeding additionally, but the intracerebral hemorrhage must be considered the most clinically significant bleed at the time of enrollment.
- 4. Performance of a head CT or MRI scan demonstrating the intracerebral bleeding within 2 hours prior to randomization (the baseline scan may be repeated only once to meet this criterion).
- 5. Treatment with an oral FXa inhibitor (apixaban [last dose 2.5 mg or greater], rivaroxaban [last dose 10 mg or greater], or edoxaban [last dose 30 mg or greater]:
 - $\circ \leq 15$ hours prior to randomization.

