10.5. Efficacy Endpoints and Analyses

10.5.1. Population

The primary, secondary, and additional efficacy endpoints will be analyzed using the ITT population.

10.5.2. Definitions

Hemostatic efficacy will be determined by the blinded EAC. Cases will be primarily determined to have effective hemostasis (i.e., a rating of "good" or "excellent") or not (i.e., a rating of "poor/none") based on pre-specified criteria documented in the Adjudication Charter and summarized in Appendix B.

For biomarker endpoints, the baseline measurement will be the most recent value drawn within 120 minutes prior to randomization. Any baseline measurement collected greater than 120 minutes prior to randomization will be considered out of window.

10.5.3. Efficacy Endpoints

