10.5.3.1. Primary Efficacy Endpoint

The primary efficacy endpoint is based on the achievement of effective hemostasis 12 hours post-randomization, as determined by the blinded EAC, based on pre-specified criteria documented in the Adjudication Charter (see Appendix B).

Effective hemostasis will be further defined as:

- 1 = for patients with hemostatic efficacy rated by the EAC as excellent or good, and
- 0 = for patients with hemostatic efficacy rated by the EAC as poor/none.

For a patient to have excellent or good hemostatic efficacy, he or she must meet all of the following criteria:

- NIHSS score of less than +7 point change from the baseline score at 12 hours post-randomization.
- No greater than 35% increase from baseline in hematoma volume within 12 hours post-randomization.
- Has not received rescue therapy (as defined in Section 7.2, Section 7.3, and Section 7.4) between 3 and 12 hours post-randomization

If data supporting either the imaging or clinical components of the adjudication of hemostatic efficacy are missing, out-of-window, uninterpretable or confounded (e.g., intubation or sedation), cases will be referred for external adjudication by EAC. Procoagulant blood products administered within 3 hours post-randomization to patients randomized to andexanet will be reviewed by EAC to determine if they were related to clinical or administrative reasons. Surgeries or procedures impacting hematoma volume within 3 hours post-randomization will also be reviewed by EAC to determine if related to clinical or administrative reasons (see Section 7.2, Section 7.3, and Section 7.4).

Cases where it is determined that there is insufficient information, or when it is not otherwise possible to properly assess the effect of treatment, will be further classified by the EAC as 'non-evaluable due to administrative reasons' (e.g., follow-up scan not available/ performed/ interpretable, patient transferred to another facility for administrative purposes) or 'non-evaluable due to clinical reasons' (e.g., patient died, patient had unplanned surgery draining hematoma).

All ITT patients will be included in the primary analysis. Patients with non-evaluable hemostatic efficacy due to clinical reasons will be treated as treatment failures (similar to patients with poor/none hemostatic efficacy). Both non-evaluable subjects due to administrative and clinical reasons will be included in the denominator for primary efficacy analysis.

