Because of the critical nature of the illness under study and the possibility that patients will be unable to provide their own consent, proxy consents (defined as consent from an LAR) and/or emergency consents (defined as consent from a qualified medical professional) are allowed if permissible by local or regional laws and regulations.

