4. ANALYSIS SETS

The analysis sets to be included are shown in Table 2.

-				
Analysis Set	Description			
Screened Set	All participants who signed an informed consent form.			
ES	All participants who signed an informed consent form; screen failures are excluded.			
ITT Set	All participants randomized to study intervention. Participants will be analyzed according to the study intervention they are randomized to. Participants who are randomized without signing the consent form throughout the study will not be included in the ITT Set.			
SS	All randomized participants who received at least 1 dose of the study intervention. In the usual care arm, randomized participants who received no treatment will also be part of the SS. Participants will be analyzed according to the study intervention they actually received.			
PPS	The PPS will include all participants in the ITT Set who did not have important protocol deviations that impact the primary efficacy assessment. Detailed rules on how to define the PPS are located in Section 6.1.			

Table 2:Analyses Sets

Abbreviations: ES=Enrolled Set; ITT=Intent-to-Treat; PPS=Per-Protocol Set; SS=Safety Set

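### The set called ITT omits randomized patients for whom consent is never signed; with deferred consent and open allocation this is a post-randomization exclusion that no planned analysis reverses

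*Protocol*

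**What the plan says.** Protocol 10.4.2 opens with the usual definition, "The ITT Population will include all randomized patients according to the randomized treatment", and narrows it in the next sentence: "Participants who are randomized without signing the consent form throughout the study will not be included in the ITT set". SAP Section 4, Table 2, has the same exclusion: "Participants who are randomized without signing the consent form throughout the study will not be included in the ITT Set". Protocol 10.5.1 applies the set to every efficacy endpoint: "The primary, secondary, and additional efficacy endpoints will be analyzed using the ITT population". Protocol 10.5.3.1 adds: "All ITT patients will be included in the primary analysis".

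Consent may come after randomization. Under Inclusion Criterion 1 (Protocol 4.1), "Deferred consent procedure is allowed where approved by local ethics committees", and where the patient has not signed before entry, "informed consent from the patient (or LAR) will be obtained as soon as realistically possible after inclusion in the trial". Protocol 12.2 widens the routes where local law permits: "proxy consents (defined as consent from an LAR) and/or emergency consents (defined as consent from a qualified medical professional) are allowed".

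Within the ITT set, the plan keeps losses in the denominator. Protocol 10.5.3.1 counts patients who are non-evaluable for clinical reasons, death included, as treatment failures. SAP 5.3.1 and 6.1 score administrative non-evaluables as poor/none as well.

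**The concern.** An intention-to-treat comparison is protected by randomization only if membership of the set does not depend on what happens afterwards. Under deferred consent it does. Protocol 3.1 and 6.2 have andexanet started within 30 minutes of randomization, and Protocol 3.2.2 leaves the investigator and most of the site team unblinded. A patient may die before anyone signs, or a patient or representative may decline once the allocation and early course are known. Either can depend on arm, outcome or both.

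The rule also departs from the plan's own approach. A death or missing scan inside the set counts as a failure, whereas a death before any signature leaves the analysis. If such losses were related to outcome and unequal by arm, the primary difference would no longer compare the groups as randomized, at the interim or the final analysis.

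**Working it through.** **Inputs.** From Protocol 10.3, 10.5.4.2 and 10.7: effective hemostasis 80% andexanet and 70% usual care; 450 per arm; one interim at 50%; nominal two-sided levels 0.0310 and 0.0277. The share of patients never consented is in neither document, so every share below is an assumption.

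**1. The plan's own figures.** Pocock-type Lan-DeMets spending at half information is 0.05 × ln(1 + (e − 1) × 0.5) = 0.0310. A bivariate normal with correlation √0.5 then gives 0.0277 at the final. Two-look power with a pooled-variance, unstratified statistic is 90.9% with no dropout and 90.0% with an assumed 3%. The stated 90% reproduces. The smallest significant final difference is about 2.201 × √(0.75 × 0.25 × 2/450) = 2.201 × 0.02887 = 0.0635, or 6.4 points.

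**2. What a reported 10.0 points means in all randomized.** Let eA and eU be the excluded shares, and sA and sU the success rates among the excluded. Then

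D = [(1 − eA) × 0.80 + eA × sA] − [(1 − eU) × 0.70 + eU × sU].

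| eA | eU | Outcome of the excluded | D |
|---|---|---|---|
| 3% | 1% | all failed | 0.776 − 0.693 = 8.3 points |
| 3% | 1% | half failed | 0.791 − 0.698 = 9.3 |
| 3% | 1% | same rates as those kept | 0.800 − 0.700 = 10.0 |
| 3% | 1% | worst case: andexanet failed, usual care succeeded | 0.776 − 0.703 = 7.3 |
| 5% | 2% | all failed | 0.760 − 0.686 = 7.4 |
| 2% | 5% | all failed | 0.784 − 0.665 = 11.9 |
| 3% | 3% | all failed | 0.776 − 0.679 = 9.7 |

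The bias needs exclusion to be related to outcome, and imbalance between arms is what makes it material. Its sign follows the imbalance.

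**3. No true effect (70% in both arms).** With one success rate s among the excluded, the apparent difference is (0.70 − eA × s)/(1 − eA) − (0.70 − eU × s)/(1 − eU).
- 5% vs 2%, all failed: 0.7368 − 0.7143 = +2.3 points. With half failed: 0.675/0.95 − 0.690/0.98 = +0.6.
- 3% vs 1%, all failed: 0.7216 − 0.7071 = +1.5 points. The chance of a false andexanet win rises from 2.5% to 6.3%.
- 5% vs 5%, all failed: 0.0 points, and the chance stays at 2.5%.

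**4. Near a boundary, a few patients matter** (tables chosen to lie close to it; unstratified test).
- Interim: 177/225 vs 158/225 gives p = 0.040. Removing two andexanet failures gives p = 0.026, below 0.0310.
- Final: 344/450 vs 315/450 gives p = 0.0290. Removing one gives p = 0.0250, below 0.0277.

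**5. Does any planned output restore them?** In SAP 5.3.3, analyses 1, 3 and 4 use the ITT set or a subset of it, analysis 2 uses the PPS (itself within ITT), and analysis 5 changes only the strata. None does. SAP 5.2.1 tabulates numbers randomized and numbers in the ITT set by treatment and lists set status by participant, so the count lost per arm can be found by subtraction. The reasons cannot. The Safety Set (Protocol 10.4.1; SAP Table 2) has no consent condition, so as written a treated patient can be in the safety mortality summaries and absent from the efficacy analysis.

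**The case against.** The strongest reply is that few patients should be affected and that part of the rule may be a legal necessity. Deferred consent applies only where ethics committees approve it, and the protocol's overview of changes records a US version without it. A representative's signature, or emergency consent where permitted, keeps a patient in the set, so an early death with a representative's consent on file still counts as a failure. Eligibility excludes GCS below 7 and NIHSS above 35, and the mortality above 30–40% cited in Protocol 1.0 is at 30 days, not 12 hours. Where consent is refused, the sponsor may have no right to use the data. All of this stands and limits the size of the problem. It does not remove the selection or supply an analysis that tests it.

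Three stronger readings are tempting but unsupported.
- *Patients consented only by a representative are excluded.* Protocol 4.1 and 12.2 treat patient or representative signature as consent, and SAP Table 2 uses the same shorthand about participants signing for the Screened and Enrolled Sets.
- *The rule deletes failures.* The exclusion runs through the whole study while the endpoint is at 12 hours. A patient who refuses or dies later without consent may have been a 12-hour success.
- *The losses are invisible.* SAP 5.2.1 shows them by arm.

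**Conclusion.** The point holds in limited form. The primary set is not all randomized patients: it omits those for whom no patient, representative or permitted emergency consent is ever signed. Under deferred consent and open allocation, that is a post-randomization exclusion which may differ by arm. The documents do not show that it favours andexanet or that it inflates type I error in this trial. If exclusion is unrelated to outcome the bias is zero, and 3% in each arm, all failures, costs 0.3 points. At an assumed 3% vs 1%, a reported 10.0 points becomes 8.3 if every excluded patient failed and 9.3 if half did. That is modest against the smallest significant difference of about 6.4 points, but it could decide a result near a boundary. The gap in the plan is the lack of stated reasons and of any analysis that returns these patients. It should be closed before unblinding.

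**What to change.** 1. Keep in ITT the patients who die before consent can be obtained, where ethics approval allows use of their data. Score them under the existing rule for cases non-evaluable for clinical reasons. State in the definition that a representative's or permitted emergency consent counts as signed.
2. For patients whose data may not be used, add the reason for exclusion, by arm and stratum, to the disposition table in SAP 5.2.1. Add a sensitivity analysis of all randomized patients that returns them as poor/none in both arms, and a second using the worst-case rule already defined in sensitivity analysis 4. Both need only allocation, stratum and counts, not clinical data.
3. If the exclusion stays, call the set modified ITT and reconcile it with the Safety Set.

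The cost is a wording change in both documents and one extra analysis in two versions. Power is slightly lower when these patients are counted as failures in both arms: 89.8%, 87.3% and 84.7% at assumed shares of 1%, 3% and 5%, against 90.6%, 90.0% and 89.4% if the same shares are excluded without relation to outcome. Poor/none scoring may also misclassify refusers who were 12-hour successes, so in step 2 it belongs in a sensitivity analysis and not in the primary.

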10.5. Efficacy Endpoints and Analyses

10.5.1. Population

The primary, secondary, and additional efficacy endpoints will be analyzed using the ITT population.

10.5.2. Definitions

Hemostatic efficacy will be determined by the blinded EAC. Cases will be primarily determined to have effective hemostasis (i.e., a rating of "good" or "excellent") or not (i.e., a rating of "poor/none") based on pre-specified criteria documented in the Adjudication Charter and summarized in Appendix B.

For biomarker endpoints, the baseline measurement will be the most recent value drawn within 120 minutes prior to randomization. Any baseline measurement collected greater than 120 minutes prior to randomization will be considered out of window.

10.5.3. Efficacy Endpoints

10.5.3.1. Primary Efficacy Endpoint

The primary efficacy endpoint is based on the achievement of effective hemostasis 12 hours post-randomization, as determined by the blinded EAC, based on pre-specified criteria documented in the Adjudication Charter (see Appendix B).

Effective hemostasis will be further defined as:

- 1 = for patients with hemostatic efficacy rated by the EAC as excellent or good, and
- 0 = for patients with hemostatic efficacy rated by the EAC as poor/none.

For a patient to have excellent or good hemostatic efficacy, he or she must meet all of the following criteria:

- NIHSS score of less than +7 point change from the baseline score at 12 hours post-randomization.
- No greater than 35% increase from baseline in hematoma volume within 12 hours post-randomization.
- Has not received rescue therapy (as defined in Section 7.2, Section 7.3, and Section 7.4) between 3 and 12 hours post-randomization

If data supporting either the imaging or clinical components of the adjudication of hemostatic efficacy are missing, out-of-window, uninterpretable or confounded (e.g., intubation or sedation), cases will be referred for external adjudication by EAC. Procoagulant blood products administered within 3 hours post-randomization to patients randomized to andexanet will be reviewed by EAC to determine if they were related to clinical or administrative reasons. Surgeries or procedures impacting hematoma volume within 3 hours post-randomization will also be reviewed by EAC to determine if related to clinical or administrative reasons (see Section 7.2, Section 7.3, and Section 7.4).

Cases where it is determined that there is insufficient information, or when it is not otherwise possible to properly assess the effect of treatment, will be further classified by the EAC as 'non-evaluable due to administrative reasons' (e.g., follow-up scan not available/ performed/ interpretable, patient transferred to another facility for administrative purposes) or 'non-evaluable due to clinical reasons' (e.g., patient died, patient had unplanned surgery draining hematoma).

All ITT patients will be included in the primary analysis. Patients with non-evaluable hemostatic efficacy due to clinical reasons will be treated as treatment failures (similar to patients with poor/none hemostatic efficacy). Both non-evaluable subjects due to administrative and clinical reasons will be included in the denominator for primary efficacy analysis.

To evaluate the robustness of the primary efficacy results, sensitivity analyses will be performed. Further details will be provided in the SAP.

10.5.3.2. Secondary Efficacy Endpoint

The secondary efficacy endpoint is:

• Percent change from baseline to nadir in anti-fXa activity during the first 2 hours post-randomization.

Missing data for anti-fXa activity will be imputed using the multiple imputation method described by Rubin (1976) [30].

10.5.3.3. Additional Efficacy Endpoints

The additional efficacy endpoints include the following:

- Change from baseline in thrombin generation parameters (with ETP as the primary measure) obtained at 1 and 12 hours post-randomization.
- Proportion of neurologic deterioration, as defined by NIHSS increase ≥ 4 or a GCS score decrease ≥ 2 at 24 hours post-randomization versus baseline.
- Change from baseline in mRS score at 30 days post-randomization.
- Change from baseline in NIHSS score obtained at 2, 3, 6, 12, 24, and 72 hours post-randomization.
- Change from baseline GCS score obtained at 2, 3, 6, 12, 24, and 72 hours post-randomization.
- Proportion of patients with a ≥ 7-point increase from baseline in NIHSS at 12 hours post-randomization.
- Hemostatic efficacy evaluated using only imaging parameters.
- Proportion of patients receiving rescue therapy between 3 and 12 hours post-randomization.
- Correlation analysis between anti-fXa activity and the achievement of hemostatic efficacy.
- Health-related quality of life as assessed by the EQ-5D questionnaire at 30 days post-randomization.
- UW-mRS score at 30 days post-randomization.

10.5.4. Statistical Methodology for Efficacy Endpoint Analyses

10.5.4.1. Control of Family-Wise Error Rate

A combination of a hierarchical testing procedure and Hochberg Procedure will be used to test the primary and the secondary endpoint.

For the interim analysis, a hierarchical testing procedure will be used to test the primary and the secondary endpoint. The primary endpoint will be tested at an alpha level of 0.031. If the primary endpoint is statistically significant, the secondary endpoint will be tested at an alpha level of 0.031.

The final analysis is controlled in a similar fashion, using an alpha level of 0.0277.

The overall family-wise error rate is controlled at alpha level of 0.05, and accounts for the interim and final analyses for the primary and secondary endpoints.

10.5.4.2. Primary Efficacy Endpoint Analysis

The primary objective of the study is to compare the proportion of patients with effective hemostasis (excellent or good as adjudicated by the blinded EAC) between and exanet and usual care. The following hypothesis will be evaluated:

Ho: $\pi_{UC} - \pi_{andexanet} = 0$ HA: $\pi_{UC} - \pi_{andexanet} \neq 0$

Analysis will be performed using a Cochran-Mantel Haenszel (CMH) test stratified by time from symptom onset to baseline imaging scan (< 180 minutes vs. \geq 180 minutes). The corresponding 95% confidence intervals (CIs) for the difference in proportions, and the proportions from the two groups, will be provided.

The study will be considered to meet its primary efficacy objective if the proportion of and exanet-treated patients with effective hemostasis (excellent or good as adjudicated by the independent EAC) is significantly higher (p < 0.031 at the interim analysis, OR p<0.0277 at the final analysis) than the proportion of patients with effective hemostasis randomized to usual care.

A sensitivity analysis will be performed using a CMH test stratified by intended-usual-care-agent and time from symptom onset to baseline imaging scan.

Further details of the primary analysis will be provided in the SAP.

